3.2.1 Number of subjects required to be included in the study

The study will enroll up to 2,000 patients with successful SJM CRT MP device implant from up to 140 centers undergoing CRT implantation. Any patient who received a market approved SJM Quadra Allure MP, Quadra Assura MP, or newer SJM CRT MP device is eligible for enrollment in the study.

3.2.2 Estimated time needed to enroll this subject population

[REDACTED]

3.3 Objectives

The objective of this post-market study is to understand the use of the MPP technology in real-world clinical practice. The study should provide an understanding of the impact of MPP technology on:

Clinical Investigational Plan

- Overall CRT response rate measured by CCS. (A responder is defined as improved or unchanged from baseline and non-responder is defined as worsened from baseline.)
- QOL, LVEF, if available and LVESV, if available
- Programming timing and workflow
- Rates of HF hospitalization events, cardiovascular hospitalizations, and HF 30-day hospitalization rates
- Costs associated with HF-related healthcare utilizations
- All-cause mortality

3.4 Inclusion and Exclusion Criteria

A subject, who meets all of the inclusion criteria, and none of the exclusion criteria, is eligible to participate in this study.

3.4.1 Inclusion Criteria

*Eligible patients will meet **all** of the following:*

- Are scheduled to receive a new CRT implant or an upgrade from an existing ICD/Pacemaker implant (SJM CRT MP device and SJM QUAD Lead) with no prior LV lead placement
- Have the ability to provide informed consent for study participation and are willing and able to comply with the prescribed follow-up tests and schedule of evaluations

3.4.2 Exclusion Criteria

*Patients will be excluded if they meet **any** of the following:*

- Are expected to receive a heart transplant during the duration of the study
- Have an epicardial ventricular lead system (Active or Inactive)
- Are less than 18 years of age
- Are currently participating in a clinical investigation including an active treatment arm and belong to the active arm
- Are not expected to complete the study follow-up schedule or duration due to any health condition other than heart failure, such as malignancy, indication for heart transplant or hospice care.

3.5 SUBJECT POPULATION

3.5.1 Subject Screening

All subjects presenting at the investigational site should be screened by a member of the investigational team previously trained on the CIP and delegated to do so.

Subjects who do not meet the inclusion criteria or do meet the exclusion criteria will not be eligible to participate in this study.

Clinical Investigational Plan

3.5.2 Point of Enrollment

All subjects who meet inclusion criteria, do not meet exclusion criteria, sign an IRB/EC approved informed consent, complete a Baseline visit prior to device implant and have an attempted implant of the SJM Quadra Allure MP, Quadra Assura MP, or newer SJM CRT MP device will be considered enrolled in the study.

3.6 INFORMED CONSENT PROCESS

3.6.1 General process

Prior to enrolling in the clinical study and conducting study-specific procedures, all subjects will be consented, as required by applicable regulations and the center's IRB/EC. Informed consent must be obtained from each subject prior to any study-related procedures. The consent form must be signed and dated by the subject and by the person obtaining the consent.

The principal investigator or his/her authorized designee will conduct the Informed Consent Process. This process will include a verbal discussion with the subject on all aspects of the clinical study relevant to the subject's decision to participate in the clinical study.

The subject shall be provided with the informed consent form written in a language understandable to the subject and approved by the center's IRB/EC. Failure to obtain informed consent from a subject prior to study enrollment should be reported to St. Jude Medical within 5 working days and to the reviewing center's IRB/EC consistent with the center's IRB/EC reporting requirements.

4.0 DEVICE

4.1 Device Description

In this study, the Quartet™ LV family of leads will be implanted with the SJM CRT MP device. The SJM CRT MP devices are supported by the St. Jude Medical Merlin™ Patient Care System (Merlin™ PCS) with software Model 3330 version 21.1.1 rev 1 (or higher).

The Quartet™ family of LV lead is a quadripolar, over-the-wire design that enables implantation using either a stylet or guidewire. The lead has an open lumen and an opening at the lead tip to allow the use of a guidewire. The body of the leads has Optim™ insulation.

The titanium nitride (TiN) coated platinum/iridium (PtIr) tip electrode on the lead contains a molded ring that elutes steroid. Additionally, the surface of the tip electrode is coated with a thin steroid film to provide immediate steroid release. Three TiN-coated PtIr ring electrodes are located on the lead.

[figure not shown]
Clinical Investigational Plan

The lead provides pace/sense capability from 4 electrodes (tip and 3 rings):

- Distal Tip (D1)
- Mid 2 (M2)
- Mid 3 (M3)
- Proximal 4 (P4)

The Quartet™ family of LV leads can be programmed with a combination of 10 – 14 possible pacing vectors using the Merlin™ PCS programmer. Vectors are presented as cathode-anode (Figure 1)

Figure 1: SJM CRT MP Device with Quadripolar Technology: LV Lead Vector (10 CRT-D or 14 CRT-P VectSelect Quartet™ Vectors)

Please note Vector numbering is for protocol use only and is not reflected on the Merlin™ programmer screen.

Clinical Investigational Plan

The user has the option to program the device to MPP in addition to BiV pacing. MPP consists of delivering two sequential LV pulses (LV1 and LV2) in addition to the standard RV pulse as follows:

- RV first: $RV \xrightarrow{D1} LV1 \xrightarrow{D2} LV2$
- LV first: $LV1 \xrightarrow{D1} LV2 \xrightarrow{D2} RV$

LV1 and LV2 configurations can be chosen from any of the 1 – 14 pacing vectors listed in Figure 1 with independent pacing characteristics. Additionally, the timing delay 1 (D1) can be programmed from 5ms to 80ms with 5ms steps and the timing delay 2 (D2) can be programmed from 5ms to 50ms with 5ms steps, respectively.

4.2 Device Handling & Storage

Instructions for use, storage and handling instructions, preparation for use and any precautions can be found in the User's Manuals for each of the market-released devices and leads.

[figure not shown]

Clinical Investigational Plan

5.0 PROCEDURES

5.1 Study Flow Chart

Figure 2: Flow Chart

*The implant procedure is not considered part of the research study.

Clinical Investigational Plan

5.2 Evaluation of responder status

Patients' responder status will be assessed at 3, 6 and 12 months post implant using the CCS. The CCS includes four components: NYHA class, Patient Global Assessment (PGA), HF events, and cardiovascular death.²¹

The **NYHA Class assessment and PGA** are determined by a designated assessor interviewing patients about their symptoms. Specifically, the PGA will be a single interview question asking the patient to categorize how they feel compared to their previous visits as either:

- Markedly better
- Better
- No change
- Worse
- Markedly worse

At the 3, 6 and 12-month visits, a PGA will be conducted to evaluate how the patient feels compared before having the CRT system implanted.

In this trial, a **HF event** is defined as any one of the following when the subject has symptoms and/or signs consistent with congestive heart failure:

- Hospitalization for HF \geq 24 hours
- Clinic or hospital visit for HF < 24 hours (i.e. outpatient treatment, observational care, ER, Urgent Care and physician's office visit) requiring administration of IV diuretics, inotropes, and/or vasodilators

Finally, **cardiovascular death** is defined as sudden unexpected death; heart failure death; myocardial infarction related death; or 'other' death, such as deaths due to pulmonary embolism, peripheral thromboembolism, stroke, vascular procedure, or other major cardiovascular event.

Using the CCS and decision algorithm described in section 5.2.1 patients are categorized as Improved, Worsened or Unchanged based on the following rules:

- “Improved” – patients demonstrating:
 - At least a one-class improvement in NYHA Class OR improvement by PGA (“better” or “markedly better”)
AND
 - No HF events as described above
AND
 - No cardiovascular death
- “Worsened” – patients demonstrating:
 - Worsening in NYHA Class OR worsening by PGA (“worse” or “markedly worse”)

OR

[figure not shown]

Clinical Investigational Plan

- Presence of HF events as described above
OR
 - Cardiovascular death
- “Unchanged” – patients neither “Improved” nor “Worsened”.

Patients who are “Improved” or “Unchanged” using the above definition will be grouped together as Responders. Patients classified as “Worsened” will be considered Non-Responders.

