1.0 SYNOPSIS

Title:	MultiPoint™ Pacing (MPP) Post Market Study
Acronym:	MPP PMS
Purpose:	The purpose of this post market study is to characterize real-world use of MPP technology in patients indicated for a cardiac resynchronization therapy (CRT) device.
Objectives:	
The primary objective of this post market study is to understand the use of the MPP technology in real-world clinical practice. The study should provide an understanding of the impact of MPP technology on:
 
 • Overall CRT response rate measured by Clinical Composite Score (CCS). (A responder is defined as improved or unchanged from baseline and non-responder is defined as worsened from baseline.) • Quality of Life (QOL), left ventricular ejection fraction (LVEF, if available) and left ventricular end systolic volume (LVESV, if available) • Programming timing and workflow • Rates of heart failure (HF) hospitalization events, cardiovascular hospitalizations, and HF 30-day hospitalization rates • Costs associated with HF-related health care utilizations • All-cause mortality
Design:	
This is a prospective, multicenter, non-randomized registry/observational study. The study will enroll up to 2,000 patients with successful SJM CRT MP device implant from up to 140 centers undergoing CRT implantation. Any patient who received a market approved SJM Quadra Allure MP, Quadra Assura MP, or newer SJM CRT MP device is eligible for enrollment in the study. MPP programming guidance will be specified in the protocol. Patients will be followed for 12 months after implant. Data will be collected at Baseline (within 30 days prior to implant), Post-Implant (within 30 days following successful CRT device implant), 3, 6, 12 months and during any unscheduled follow-up visit.
 
[REDACTED]

Devices used:	Market-approved SJM Quadra Allure MP, Quadra Assura MP device, or newer SJM CRT MP device and market-approved SJM Quadripolar LV lead
Study Population	All subjects who meet inclusion criteria, do not meet exclusion criteria, sign an IRB/EC approved informed consent, complete a Baseline visit prior to device implant and have an attempted implant of the SJM Quadra Allure MP, Quadra Assura MP, or newer SJM CRT MP device will be considered

[figure not shown]
Clinical Investigational Plan

	enrolled in the study.

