Inclusion/Exclusion Criteria	
Inclusion Criteria Eligible patients will meet all of the following:
 
 • Are scheduled to receive a new CRT implant or an upgrade from an existing ICD/Pacemaker implant (SJM CRT MP device and SJM QUAD Lead) with no prior LV lead placement • Have the ability to provide informed consent for study participation and are willing and able to comply with the prescribed follow-up tests and schedule of evaluations 
Exclusion Criteria Patients will be excluded if they meet any of the following:
 
 • Are expected to receive a heart transplant during the duration of the study • Have an epicardial ventricular lead system (active or inactive) • Are less than 18 years of age • Are currently participating in a clinical investigation including an active treatment arm and belong to the active arm • Are not expected to complete the study follow-up schedule or duration due to any health condition other than heart failure, such as malignancy, indication for heart transplant or hospice care.
Data Collection	
All patients will complete a Baseline visit within 30 days prior to implant. During this visit, inclusion/exclusion criteria evaluation, informed consent, NYHA class, QOL questionnaires (Minnesota Living with Heart Failure – MLWHF and EQ-5D) will be completed. All subjects will undergo SJM CRT MP device implant per standard of care. Device measurements will be collected within 30 days of successful SJM CRT MP device implant during the Post-implant visit. Patients will be followed for 12 months after successful CRT implant. Follow-up data will be collected at 3, 6 and 12 months post implant and during any unscheduled follow-up visits. During the study mandated follow-up visits, arrhythmic episode diagnoses, device data, stored electrograms, LVEF (if available), LVESV (if available), NYHA class, Patient Global Assessment (PGA), and QOL questionnaires (Minnesota Living with Heart Failure – MLWHF and EQ-5D) will be collected. All clinical events for cardiovascular reasons, such as hospitalizations and emergency room visits, will also be collected. All study data, including device data and stored electrograms, will be sent to SJM via the electronic data capture (EDC) system.

Clinical Investigational Plan

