3.2 Study Design and Scope

This is a prospective, multicenter, non-randomized registry/observational study. All subjects who meet inclusion criteria, do not meet exclusion criteria, sign an IRB/EC approved informed consent, complete a Baseline visit prior to device implant and have an attempted implant of the SJM Quadra Allure MP, Quadra Assura MP, or newer SJM CRT MP device will be considered enrolled in the study. MPP programming guidelines are provided in Appendix I. Patients will be followed for 12 months after implant. Data will be collected at post-implant (within 30 days of successful CRT device implant), 3, 6, 12 months and during any unscheduled follow-up visit. At 12 months, the responder rate will be evaluated among the following groups:

- MPP Group: MPP ON within 1 month post implant and then continuously programmed ON until 12 months (i.e., MPP ON for months 1-12 continuously)
- Treatment Strategy (BiV/MPP) Group: MPP ON at the 12-month study visit and for at least 3 continuous months prior to 12-month assessment (i.e., BiV ON at some point in months 1-9 and MPP ON for months 10-12)
- BiV Group: MPP OFF at the 12-month study visit and for at least three continuous months prior to 12-month assessment (i.e., BiV ON for months 10-12)
- Other Pacing Group: Other pacing schemes not covered above (Retrospective categorization implemented based on the usage of MPP or BiV for 12 months)

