5.2.1 Decision algorithm to classify response to CRT treatment

5.3 PROCEDURES

The clinical study will be conducted in accordance with the CIP. All parties participating in the conduct of the clinical study will be qualified by education, training, or experience to perform their tasks and this training will be documented appropriately.

The clinical study will not commence until St. Jude Medical receives written approval from the IRB/EC and relevant regulatory authorities and all required documents have been collected from the site(s).

Clinical Investigational Plan

Table 1: List of all study specific activities/procedures

Evaluation	Baseline*	Post-Implant**	3-month Visit	6-month visit	12-month visit
Inclusion/Exclusion Evaluation and Informed Consent	√				
NYHA class	√ §		√	√	√
Patient Global Assessment			√	√	√
MLWHF and EQ-5D questionnaires	√		√	√	√
LVEF (if available) and LVESV (if available)	√		√	√	√
Cardiac Medications List	√				
HF events		√	√	√	√
LV lead capture threshold testing and pacing lead impedance		√ Testing of programmed LV lead vector(s) required	√ Testing of programmed LV lead vector(s) required	√ Testing of programmed LV lead vector(s) required	√ Testing of programmed LV lead vector(s) required
RA, RV capture threshold, signal amplitude and pacing lead impedance testing		√	√	√	√
Device Session Records		√	√	√	√

* Baseline visit should be completed up to 30 days before device implant to be enrolled in the study

** Post-implant visit can occur up to 30 days post successful SJM CRT MP device implant

§ At Baseline visit, NYHA used for device eligibility will be collected on the CRF

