5.4 ENROLLMENT

5.4.1 Baseline visit

Patients will undergo screening evaluations as outlined by the inclusion/exclusion criteria. The principal investigator or delegated study personnel are responsible for screening all potential patients to determine eligibility for the study.

All patients will complete a Baseline visit within 30 days prior to implant. During this visit, eligible patients will sign an IRB/EC-approved informed consent form. NYHA class used to

Clinical Investigational Plan

determine device eligibility will be collected on the Case Report Form (CRF). All patients will also complete QOL questionnaires (MLWHF and EQ-5D) at this visit prior to device implant. If a 2D-Echocardiogram was conducted as part of patient's standard of care, LVEF and LVESV values will be collected on the CRF.

Baseline, Medication, MLWHF and EQ-5D questionnaire CRFs will be submitted to St. Jude Medical using the EDC system.

[figure not shown]

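### Section 5.2 gives the single Patient Global Assessment question two conflicting reference points: previous visits, and before CRT implant

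*Combined protocol and SAP*

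**What the plan says.** Section 5.2 defines response by the Clinical Composite Score (CCS), which combines NYHA class, the PGA, heart failure events and cardiovascular death. The PGA is a single interview question with five answers, from markedly better to markedly worse.

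The section states the reference point twice:

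- When it introduces the question, it describes it as "asking the patient to categorize how they feel compared to their previous visits as either" one of the five grades.
- Directly after the list of answers, it says that at the 3-, 6- and 12-month visits "a PGA will be conducted to evaluate how the patient feels compared before having the CRT system implanted".

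The same section then makes "Worsening in NYHA Class OR worsening by PGA" one of the conditions for the Worsened category, and Worsened patients are non-responders. The Synopsis and section 3.3 both give the overall definition: "A responder is defined as improved or unchanged from baseline and non-responder is defined as worsened from baseline". Section 3.2 sets the use of the result: "At 12 months, the responder rate will be evaluated among the following groups". Section 12.1 reports the 12-month response rate as a percentage with an exact 95% confidence interval.

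**The concern.** A change-type question has no meaning without its reference point, and here one question has two. *Before implant* is a fixed point. *Previous visits*, in the plural, is not: by the time of a 12-month interview it could mean Baseline, the post-implant visit, the 3-month visit, the 6-month visit or an unscheduled visit.

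If assessors at some sites, or the form itself, ask about change since the last visit, the 12-month answer measures recent change and not change since CRT was started. It would then feed a response rate that the protocol defines against baseline. Response is the first-listed objective and is evaluated among the pacing groups.

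The PGA records only a relative answer. An answer given against the wrong reference point cannot be converted afterwards to the right one.

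**Working it through.** The plan states no figure that depends on this point, so there is none to reproduce. The check is a comparison of texts, followed by a count from the section 5.2 rules.

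**Step 1: do the two sentences govern the same assessments?** Table 1 in section 5.3 and section 5.5 place the PGA at 3, 6 and 12 months only. There is no other PGA visit to which the first sentence could apply, so both describe the same three interviews.

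**Step 2: do the two reference points differ at those visits?** Scheduled visits that precede each PGA, from Table 1:

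| PGA visit | Earlier scheduled visits | Number | Of these, before implant |
|---|---|---|---|
| 3 months | Baseline, post-implant | 2 | 1 (Baseline) |
| 6 months | the above and 3-month | 3 | 1 |
| 12 months | the above and 6-month | 4 | 1 |

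Section 5.4.1 fixes the one that precedes implant: "All patients will complete a Baseline visit within 30 days prior to implant". Unscheduled visits (section 5.6) may come on top. At every PGA visit, *previous visits* therefore includes at least one visit after implant.

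**Step 3: does any other visible text settle it?** The Synopsis lists "NYHA class, Patient Global Assessment (PGA), and QOL questionnaires" for the follow-up visits without a reference point. Table 1 gives none. Section 5.5 sends the reader back to section 5.2, where both sentences stand. The definition of response from baseline agrees with the pre-implant reference, but it does not say how the PGA question is to be put.

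**Step 4: can the choice change the label?** Take a patient with NYHA class unchanged, no heart failure event and no cardiovascular death. Under the section 5.2 rules:

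- Markedly better or better: Improved, so Responder.
- No change: Unchanged, so Responder.
- Worse or markedly worse: Worsened, so Non-Responder.

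That is 3 answers that give Responder and 2 that give Non-Responder. Pair the answer given against pre-implant with the answer given against the most recent visit:

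- All pairs: 5 × 5 = 25
- Responder against pre-implant, Non-Responder against the last visit: 3 × 2 = 6
- Non-Responder against pre-implant, Responder against the last visit: 2 × 3 = 6
- Discordant: 6 + 6 = 12 of 25

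**Step 5: an example.** Such a patient feels much better at 6 months and slips by 12 months, but still feels better than before implant. Against the 6-month visit the 12-month answer is *worse*, so Non-Responder. Against pre-implant it is *better*, so Responder. In the reverse case, a patient feels worse than before implant but better than at 6 months. That patient is a Responder under the last-visit reading and a Non-Responder under the pre-implant one.

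The count is limited to patients in whom the PGA alone decides. No claim is made for other patients.

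**The case against.** The best defence is that the section resolves itself. The first sentence introduces the instrument in general terms. The second is specific to the visits at which it is used, and it agrees with a definition of response that the protocol gives twice. On an ordinary reading the specific sentence governs. This stands as evidence of what was intended, and it tells the sponsor which phrase to change. It does not remove the conflict. The first sentence is the one that describes the question put to the patient, and assessors at up to 140 centers should not have to work out which sentence to follow.

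Four further points deserve weight:

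- **The harmful reading is one reading among several.** The text does not say *most recent visit*, and *previous visits* includes Baseline. This is correct, and the misclassification is therefore conditional. The open referent is also part of the fault.
- **Some rival visits are weak candidates.** The post-implant visit has no NYHA, PGA or quality-of-life assessment and may fall on the day of implant. Unscheduled visits are defined by device reprogramming. The realistic divergence is therefore mainly at 6 and 12 months. The response rate in section 12.1 is the 12-month one.
- **The figure of 12 of 25 is not an effect size.** It follows from the three-to-two split of answers and gives improbable pairs the same standing as likely ones. It shows only that the label can change in either direction.
- **The analysis is descriptive.** Section 12.1 summarizes the response rate, and no visible text plans a test between groups. Nothing shows that the wording would act differently in one pacing group than in another.

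Finally, the case report forms are kept under separate cover and the section 5.2.1 figure is not shown. Either may already carry one reference point. If the form does, the harm to the data falls away and only the protocol text is at fault.

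**Conclusion.** The point holds. Section 5.2 contradicts itself on the reference point of a component of the response endpoint, and nothing visible withdraws the wording that conflicts with the definition of response from baseline. Confidence in the conflict itself is high.

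The effect on results is unknown. It depends on how sites or the form read the question, and the documents give no PGA distribution and no rate of disagreement between the two reference points. Neither the frequency of misclassification nor its net direction can be derived. What is established is that, where NYHA class is unchanged and there are no events, the choice of reference point alone can turn a Responder into a Non-Responder or the reverse.

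This should be corrected, given that the intended reference is identifiable, the repair is small, and a wrongly anchored answer cannot be recovered later.

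**What to change.** In section 5.2, reword the description of the question so that it asks how patients feel compared with before the CRT system was implanted, in place of the reference to previous visits. Then confirm that the PGA case report form uses that same wording at 3, 6 and 12 months, and that the section 5.2.1 algorithm assumes the same reference.

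The cost is one phrase in the protocol and, only if the form differs, one change to its wording. No visit, test or staff is added. It is a minor amendment, with IRB/EC approval where section 14.0 requires it. If the form has already been used with a different reference point, the answers collected that way should be identified, because they cannot be re-anchored.
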